**Figure 1      Participant Flow**

## 2.4. Statistical Hypotheses / Statistical Analyses

The study has two primary objectives.

No formal hypothesis will be tested for the first, primary objective that assesses the safety and tolerability of GSK2831781 in participants.

The second primary study objective is to evaluate the dose-response relationship in the change from baseline in Complete Mayo score, following 10 weeks of treatment with GSK2831781 or placebo.

Due to the low number of participants in the 3 middle doses, this will be done by estimating the posterior probabilities of the difference between GSK2831781 450 mg IV and placebo, using Bayesian methodologies (Section 8.1.1 Primary Endpoint).

### 3. PLANNED ANALYSES

In line with routine pharmacovigilance, an internal GSK SRT, which will include a subset of the 204869 study team, will review blinded safety data, including clinical laboratory parameters and adverse events, at appropriate intervals during the period of study conduct. See the SRT charter for further details, including the team members of the SRT.

#### 3.1. Interim Analyses

At the interim analyses, the data will be reviewed by the DRC (Data Review Committee). Further details of the DRC remit are provided in the DRC charter which outlines how the DRC will ensure data integrity and appropriate quality control of data prior to making decisions, as well as documenting membership of the DRC.

The following interim analyses are planned to assess the safety, pharmacokinetics and efficacy of GSK2831781 in this study. Recruitment will continue while the interim analyses are being conducted, except in the case of a safety concern. Interim analysis 3 incorporates a decision for futility. Note: not all interim analyses may be conducted.

Interim Analysis	When	Objective
1 (PK)	Approximately fifteen participants (across the highest dose and placebo) have completed their pharmacokinetic assessment at Week 2.	PK will be assessed to determine if the exposures in ulcerative colitis participants are similar to those predicted based on data observed in healthy volunteers and psoriasis patients.
2 (Early Efficacy)	Approximately thirty-six participants (across the highest dose and placebo) have completed Week 10 assessments.	
Assessment of the endoscopic mucosal healing response.
 
Data will be reviewed by the DRC for internal decision making, where decision criteria are outlined in the DRC charter.
 
An assessment of futility will not be made at this point.
 
Additional data may be reviewed, including stool frequency and rectal bleeding.

3 (Efficacy futility)	Approximately sixty participants (across the highest dose and placebo) have	Assess futility based on the proportion of participants who

Interim Analysis	When	Objective
	
completed Week 10 assessments.
	
achieve endoscopic mucosal healing, based on the Mayo score.
 
The predictive probability of success at the end of the study will be calculated based on the data observed at this interim analysis.
 
The futility rule is outlined in the DRC charter and characteristics of which are included in the RAP.
 
Unblinded safety data will be reviewed.
 
Additional data may be reviewed.

4 (Pharmacodynamic)	
A minimum of approximately twenty participants per GSK2831781 dose level have completed Week 10 assessments
	
Assessment of pharmacodynamic dose-response at Week 10.
 
Data may be reviewed by the DRC for internal decision making, where decision criteria are outlined in the DRC charter.
 
An assessment of futility will not be made at this point.
 
Unblinded safety data will be reviewed.

### 3.2. Final Analyses

The final planned primary analyses will be performed after the completion of the following sequential steps:

- All participants have completed the study as defined in the protocol
- All required database cleaning activities have been completed and final database release (DBR) and database freeze (DBF) has been declared by Data Management.
- All criteria for unblinding the randomization codes have been met.
- Randomization codes have been distributed according to RandAll NG procedures.

## 4. ANALYSIS POPULATIONS

The strategy for reporting study phases is to use analysis populations to define the participants for each study phase.

### 4.1. Populations for the Induction Phase

The following analysis populations apply to the double-blind induction phase of the study.

Population	Definition / Criteria	Analyses Evaluated
Screened	
 
All participants who were screened for eligibility this includes screening failures (who never passed screening even if rescreened) and participants screened but never enrolled into the study as well as enrolled participants.
 
	
 
Study Population
 

Enrolled	
 
All participants who were randomly assigned to treatment in the study.
 
This population will be based on the treatment the participant was randomised to.
 
Any participants who receive a treatment randomisation number will be considered to have been randomised
 
	
 
Study Population
 

Safety	
 
All participants who received at least one dose of study treatment.
 
Participants who were not randomized but received at least one dose of study treatment will be listed.
 
This population will be based on the treatment the participant actually received.
 

 
	
 
Safety
 

Intent-To-Treat-Exposed (ITTE)	
 
All enrolled participants who received at least one dose of study treatment, and who have at least one valid post dose assessment.
 
This population will be based on the treatment the participant was randomised to.
 
	
 
Efficacy
 
PD
 
Biomarker
 
PRO
 

Pharmacokinetic (PK)	
 
All participants in the Safety population who had at least 1 non-missing PK assessment (Non-quantifiable [NQ] values will be considered as non-missing values).
 
	
 
PK
 

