9.3. Populations for Analyses

For purposes of analysis, the following populations are defined:

Population	Description
Enrolled	All participants who sign the ICF and were screened for eligibility.
Randomized	All participants who were randomly assigned to treatment in the study.
Safety	All randomized participants who receive at least 1 dose of study treatment.
PK	All participants in the Safety population who had at least 1 non-missing PK assessment (non-quantifiable values will be considered as non-missing values).
Intent to Treat Exposed (ITTE)	The ITTE population is defined as all participants who were randomised to treatment, who received at least one dose of study medication and who have at least one valid post dose assessment.

Population	Description
Per Protocol (PP)	
The PP Population is defined as all participants who are included in the ITTE population and are not major protocol violators with regards to inclusion/exclusion criteria, investigational product compliance and concomitant medication instructions, as defined in the RAP.
 
Participants to be excluded from the PP population will be identified prior to randomisation being unblinded or any data evaluation being performed.

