## 8.2. Secondary Efficacy Analyses

### 8.2.1. Key Secondary Endpoint

#### 8.2.1.1. Estimand

Key secondary estimand for decision making: "Composite"	
Objective:	To investigate the effect of repeat doses of GSK2831781 on clinical efficacy including endoscopic mucosal healing during the Double-Blind Induction Phase.
Estimand:	
Description
 
Difference in response rates between active doses of GSK2831781 and Placebo when added to background therapy in patients with moderate to severe, active Ulcerative Colitis.
 
Attributes
 
 
• Treatment: Placebo and active doses of GSK2831781 in addition to background therapy and stable dose of corticosteroid where relevant.
 
• Population: Patients with moderate to severe, active, Ulcerative Colitis as per inclusion/exclusion criteria.
 
• Outcome measure: Endoscopic Mucosal Healing at Week 10 assessment, where success is defined as: 
 
○ Achieving a score on the endoscopic component of the Adapted Mayo score of 0 or 1, and
 
○ Not discontinuing IP due to reasons unrelated to the COVID-19 pandemic or to sponsor's decision to terminate the study, and
 
○ Not taking medications excluded by the protocol or increasing dose of corticosteroid.
 
 
 
• Intercurrent events and strategy: 
 
○ ICE: discontinuation from IP, unrelated to COVID-19 pandemic or to sponsor's decision to terminate the study.
 
○ Strategy: included in outcome via composite strategy (i.e. post-ICE result set to non-response).
 
○ ICE: discontinuation from IP, due to COVID-19 pandemic.
 
○ Strategy: hypothetical, setting response status to missing.
 
○ ICE: discontinuation from IP, due to sponsor's decision to terminate the study.
 
○ Strategy: hypothetical, setting response status to missing.
 
○ ICE: valid endoscopy result not available, due to COVID-19 pandemic
 
 
 

Key secondary estimand for decision making: “Composite”	

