	
 
○ Strategy: hypothetical, setting response status to missing.
 
○ ICE: valid endoscopy result not available, for technical reasons
 
○ Strategy: hypothetical, setting response status to missing.
 
○ ICE: prohibited medication taken
 
○ Strategy: included in outcome via composite strategy (i.e. post-ICE result set to non-response).
 
○ ICE: increase in dose of permitted medications
 
○ Strategy: included in outcome via composite strategy (i.e. post-ICE result set to non-response).
 
● Population-level summary: Difference in proportion of participants who achieve response between placebo and relevant active doses
 

Estimation and missing data details for the key secondary estimand for decision making (“Composite”)	
	
Participants who have a missing assessment at Week 10 for reasons unrelated to the COVID-19 pandemic will be counted as non-responders in the analysis.
 
The ICEs that will be dealt with using a hypothetical strategy will have response status set to missing
 
In all cases, the missing response status will be assumed to be MAR in the statistical analysis.
 
The MAR assumption is implicit in the planned Bayesian analysis.

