2.18.	ITTE ETP	EFF_T2	Summary of Categorical Efficacy by Endpoint in Extended Treatment Phase	
Report by endpoint, visit.
 
Include the following ETP only endpoints:
 
 
• Maintained Clinical Response (Week 10 to 30 Adapted Mayo)
 
• Maintained Clinical Remission (Week 10 to 30 Adapted Mayo)
 
• Steroid Free Clinical Remission
 
• Maintained Steroid Free Clinical Remission
 
	None
2.19.	ITTE_OL_I	EFF_T2	Summary of Categorical Efficacy by Endpoint in Open Label Phase	Report by endpoint, visit.	None
2.20.	ITTE_OL_ET P	EFF_T2	Summary of Categorical Efficacy by Endpoint in Open Label Extended Treatment Phase	
Report by endpoint, visit.
 
 
•
 
	None

Efficacy: Tables					
No.	Population	IDSL / Example Shell	Title	Programming Notes	Deliverable [Priority]
2.21.	ITTE	EFF_T7	Statistical Analysis of Categorical Efficacy in Induction Phase	
Report the endpoints below, Induction phase only:
 
Endoscopic Improvement, Clinical Remission
 
Also report estimate for each level of 'Advanced Therapy experience' (i.e. subgroup)
	IA3H, SAC
2.22.	ITTE	EFF_T7	Statistical Analysis of Categorical Efficacy in Induction Phase – Sub Group	
Endoscopic Improvement and Clinical Remission only.
 
Subgroup for each level of stratification factor (advanced therapy experience)
 
Full population:
 
 
Subgroup Race and Race2
 
 
Sub-population of biologic experience:
 
 
Biologic experience type
 
 
Sub-population of TNF failure
 
 
TNF failure mechanisms
 
•
 
	None

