## CONFIDENTIAL

204869

Efficacy: Tables					
No.	Population	IDSL / Example Shell	Title	Programming Notes	Deliverable [Priority]
2.23.	ITTE	EFF_T3	Statistical Analysis of Dose Response Relationship for Categorical Endpoints	
By Endpoint then estimand.
 
 
• Endoscopic Improvement (IA4 and PC)
 
• Endoscopic Improvement, Clinical Response, Clinical Remission, ( PC only)
 
• Present analysis results for both 'Treatment Policy' and 'Hypothetical' estimands if conducted
 
	None
Histological assessments					
2.24.	ITTE	EFF_T2	Summary of Categorical Histology at each Dose Level by Endpoint in Induction Phase	
Report by endpoint, visit.
 
Geboes Histological Remission
 
RHI Remission
 
RHI Deep Remission
 
Nancy Index Remission
	SAC
2.25.	ITTE ETP	EFF_T2	Summary of Categorical Histology by Endpoint in Extended Treatment Phase	Report by endpoint, visit.	None

Efficacy: Tables					
No.	Population	IDSL / Example Shell	Title	Programming Notes	Deliverable [Priority]
Extra Intestinal Manifestations					
2.26.	ITTE	EFF_T4	Summary of Extra Intestinal Manifestations (EIMs) - Incidents by Severity, across Study Phases.	For EIMs without severity (Peripheral Arthritis and Axial Arthropathy) set levels of severity to missing  Slot early withdrawal visits to next EIM visit (there is one EIM visit at the end of each study phase)  Summary is cross-phase: Report by treatment sequence, not by treatment in an individual study phase	None
Continuous Efficacy – Pairwise Statistical Analysis					
2.27.	ITTE	EFF_T5	Statistical Analysis of Change from Baseline in Complete Mayo Score in Induction Phase		IA3H
Summaries of Efficacy after Estimand Imputations					
2.28.	ITTE	EFF_T2	Summary of Categorical Efficacy by Endpoint in Induction Phase - Estimands		IA3H, SAC
2.29.	ITTE	PD1	Summary of Mayo Score by Endpoint in Induction Phase - Estimands		SAC
2.30.	ITTE	PD1	Summary of UCEIS Total Score in Induction Phase - Estimands		SAC

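### The induction ITTE population can leave out early dropouts whom the key secondary estimand counts as non-responders

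*SAP*

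**What the plan says.** **Population.** SAP 4.1 defines ITTE for the double-blind induction phase as "All enrolled participants who received at least one dose of study treatment, and who have at least one valid post dose assessment", analysed as randomised, and assigns it to efficacy, PD, biomarker and PRO analyses. Protocol 9.3 likewise requires participants "who received at least one dose of study medication and who have at least one valid post dose assessment". Neither says what makes an assessment valid. The ITTE populations for the extended treatment and open-label phases (SAP 4.2 to 4.4) require only a dose.

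**Estimand.** The key secondary estimand (SAP 8.2.1.1) targets "Patients with moderate to severe, active, Ulcerative Colitis as per inclusion/exclusion criteria", with no condition on later assessments. For the intercurrent event "discontinuation from IP, unrelated to COVID-19 pandemic or to" the sponsor's decision to end the study, the strategy reads "included in outcome via composite strategy (i.e. post-ICE result set to non-response". The missing-data text adds: "Participants who have a missing assessment at Week 10 for reasons unrelated to the COVID-19 pandemic will be counted as non-responders in the analysis". Discontinuation due to COVID-19 or to termination, and an endoscopy unavailable because of COVID-19 or for technical reasons, are instead set to missing. SAP 8.2.2 carries these rules over to clinical remission, clinical response and symptomatic remission.

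**Displays.** In SAP 15.12.5, Table 2.21 ("Statistical Analysis of Categorical Efficacy in Induction Phase", covering endoscopic improvement and clinical remission) and Table 2.28 ("Summary of Categorical Efficacy by Endpoint in Induction Phase - Estimands") both use ITTE and are both due at the final analysis.

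**The concern.** The assessment clause is a condition that can be met or failed only after randomisation. A participant who is dosed, stops because of an adverse event or lack of effect, and provides nothing that counts as valid meets the estimand's definition of non-response but is not in the set on which the estimand is estimated. The two rules give different answers for the same person.

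What is at stake is the denominator of the composite response rates. The estimand makes early discontinuation for these reasons a failure so that it counts against the arm in which it occurs. The clause undoes that for the earliest leavers. If early loss differs between arms, the treatment difference shifts too.

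The undefined word adds a practical problem. SAP 8.2.1.1 applies valid to endoscopy results, whereas ITTE also serves analyses that use laboratory samples. Two programmers could build different populations from the same text.

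**Working it through.** No stated sample size, power or error rate depends on this clause, so there is no plan figure to reproduce. The check compares the rules and then illustrates their effect.

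**Step 1: one participant under each rule.** Dosed on Day 1; stops for an adverse event; no assessment counted as valid; no Week 10 endoscopy.

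| Rule | Result |
|---|---|
| Estimand population (SAP 8.2.1.1) | Included |
| Discontinuation rule (SAP 8.2.1.1) | Non-responder |
| Missing Week 10 rule (SAP 8.2.1.1) | Non-responder |
| ITTE (SAP 4.1, Protocol 9.3) | Excluded |
| Tables 2.21 and 2.28 (SAP 15.12.5) | Excluded, because they use ITTE |

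**Step 2: direction.** Let an arm have n dosed participants and r responders, and let k non-responders of this type be removed. The rate changes from r/n to r/(n−k), which is larger whenever r > 0 and k > 0. The difference between arms rises or falls according to which arm loses more.

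**Step 3: illustrative size.** Inputs:
- Arm sizes of 40 active and 20 placebo, from the Interim Analysis 3 paragraph of Protocol 9.2.1. They are borrowed only as plausible denominators for a terminated study.
- Placebo response of 20%, from the same place: 4/20.
- Active response of 35%: 14/40. Assumed; not in the documents.
- Numbers removed: 0 to 4 active and 0 to 2 placebo, up to 10% of each arm. Assumed.

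| Removed (active, placebo) | Active | Placebo | Difference (points) |
|---|---|---|---|
| 0, 0 (estimand rule) | 14/40 = 35.0% | 4/20 = 20.0% | 15.0 |
| 2, 1 | 14/38 = 36.8% | 4/19 = 21.1% | 15.8 |
| 4, 2 | 14/36 = 38.9% | 4/18 = 22.2% | 16.7 |
| 4, 0 | 14/36 = 38.9% | 4/20 = 20.0% | 18.9 |
| 0, 2 | 14/40 = 35.0% | 4/18 = 22.2% | 12.8 |

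For scale, the standard error of the 15.0-point difference is √(0.35×0.65/40 + 0.20×0.80/20) = 11.7 points. The two extreme shifts are therefore 3.9/11.7 = 0.33 and 2.2/11.7 = 0.19 of a standard error.

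**Step 4: Bayesian version.** This uses Beta(1/3, 1/3) for active and the SAP 15.14.1 example placebo mixture for 40% naïve, without covariates. The posterior mean difference moves from 0.167 to between 0.153 and 0.206, and P(difference > 0.10) from 0.75 to between 0.71 and 0.84. With the 60% naïve example, the mean moves from 0.150 to between 0.137 and 0.189. The 0.10 cut is chosen for illustration; the actual thresholds are not in these documents.

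**Step 5: where the clause has no effect.** The primary analysis (SAP 8.1.1.1) treats missing Week 10 scores as missing at random. A participant without post-dose data supplies no outcome to it, with or without the clause. SAP 15.12.3 restricts interim efficacy outputs to participants who completed the Week 10 visit, so anyone without a post-dose assessment is already outside the Interim Analysis 3 outputs.

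**The case against.** The best defence is that the clause rarely excludes anyone. SAP 4.1 does not say efficacy assessment, and ITTE also serves biomarkers. Soluble LAG3 is summarised in ITTE (Table 6.1) and is sampled immediately after the first infusion. On a literal reading almost every dosed participant qualifies on Day 1. Even on an efficacy reading, the bowel diary is completed daily and Table 2.7 summarises diary sub-scores in ITTE from Study Day 3, so a reader should not infer that nothing counts until the Week 2 visit. Early leavers are also asked to complete remaining visits or an Early Withdrawal visit. In addition, SAP 15.7.1 states that population definitions may exclude withdrawn participants from some outputs, and SAP 4.1 matches the protocol.

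Much of this stands, and it limits the size. It does not remove the conflict: SAP 15.7.1 discloses that exclusions may happen but does not reconcile them with the non-responder rule, and no text adopts the literal reading.

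Three stronger inferences are not supported:
- That everyone excluded is a failure under the estimand. COVID-19, termination and technical endoscopy cases are set to missing.
- That the clause inflates the treatment effect. The direction depends on the balance of losses between arms.
- That it distorts the futility decision or the primary result. Step 5 shows why not. The other planned decision point, primary completion, has no outputs planned after termination (SAP 2.1.2).

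**Conclusion.** The inconsistency is real and confined to the final composite binary analyses, chiefly endoscopic improvement and clinical remission. For participants who stop early for reasons other than COVID-19 or termination and have no valid assessment, the population rule and the estimand disagree.

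Within an arm the clause can only raise the response rate. The sign of any bias in the difference is unknown. The shift from 15.0 points to between 12.8 and 18.9 rests on an assumed active rate and assumed exclusions. The upper end is generous: it takes 10% of an arm as lost with no valid assessment at all, whereas Protocol 9.2.1 already treats total attrition of 15% as more than planned. The likely effect is small, and close to zero if a Day 1 measurement or a diary entry is accepted as valid.

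The change is still worth making. If the clause excludes nobody it does no work; if it excludes anyone in this group it contradicts the plan's own rule.

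**What to change.** In SAP 4.1, define induction ITTE as all randomised participants who received at least one dose of study treatment, analysed as randomised, by deleting the post-dose assessment condition. This matches the dose-only condition in SAP 4.2 to 4.4. Record the departure from Protocol 9.3 in SAP 2.1.1, which already lists population changes.

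Add a sentence to SAP 8.2.1.1: for the composite binary endpoints, dosed participants with no post-dose assessment count as non-responders unless a hypothetical-strategy event applies (COVID-19, sponsor termination or technical endoscopy failure).

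If the data are already unblinded, report the number affected in each arm and label the change post hoc. The planned listing of participants excluded from any population (Listing 10) is not scheduled for delivery, so these counts would need to be stated.

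The cost is wording and one population flag, with no new data and no change to the models.

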### 4.2. Populations for the Extended Treatment Phase

Population	Definition / Criteria	Analyses Evaluated
Intent-To-Treat-Exposed ETP (ITTE_ETP)	
 
All participants who received at least one dose of study treatment in the ETP (e.g. placebo or 300mg SC).
 
This population will be based on the treatment that the participant was randomised to.
 
	
 
Study Population
 
Efficacy
 
PD
 
Biomarker
 
PRO
 

Population	Definition / Criteria	Analyses Evaluated
Safety ETP	
 
• All participants who received at least one dose of study treatment in the ETP (e.g. placebo or 300mg SC).
 
• This population will be based on the treatment the participant actually received.
 
	
 
• Safety
 

Pharmacokinetic ETP (PK_ETP)	All participants in the Safety ETP population who had at least 1 non-missing PK assessment in the ETP phase (Non-quantifiable [NQ] values will be considered as non-missing values).	
 
• PK
 

#### 4.3. Populations for the Open Label Induction Phase

Population	Definition / Criteria	Analyses Evaluated
Intent-To-Treat-Exposed OL_I (ITTE OL_I)	
 
• All participants who received at least one dose of study treatment in the Open Label Induction Phase.
 
• This population will be based on the treatment that the participant was allocated to.
 
	
 
• Study Population
 
• Efficacy
 
• PD
 
• Biomarker
 
• PRO
 

Safety OL_I	
 
• All participants who received at least one dose of study treatment in the Open Label Induction phase.
 
• This population will be based on the treatment the participant actually received.
 
	
 
• Safety
 

Pharmacokinetic (PK_Ol)	
 
• All participants in the Safety_Ol_I population who had at least 1 non-missing PK assessment in Open Label Induction phase (Non-quantifiable [NQ] values will be considered as non-missing values).
 
	
 
• PK
 

